## **5.8      Duration of Therapy**

If at any time the constraints of this protocol are considered to be detrimental to the patient's health and/or the patient no longer wishes to continue protocol therapy, the protocol therapy will be discontinued and the reason(s) for discontinuation documented in the case report forms.

In the absence of treatment delays due to adverse events, treatment may continue for up to 4 doses of rhIL-7-hyFc or until one of the following criteria applies:

- Documented and confirmed disease progression
- Death
- Adverse event(s) that, in the judgment of the investigator, may cause severe or permanent harm or that rule out continuation of study drug
- General or specific changes in the patient's condition render the patient unable to receive further treatment in the judgment of the investigator
- Confirmed pregnancy
- Serious non-compliance with the study protocol
- Lost to follow-up
- Patient withdraws consent
- Investigator removes the patient from study
- The Siteman Cancer Center decides to close the study

Patients who prematurely discontinue treatment for any reason will be followed as indicated in the study calendar.

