### **5.9 Duration of Follow-up**

Patients will only be off study at the time of death. All patients will be assessed for survival by phone call, clinic visit, or medical records (e.g. physician notes/laboratory results of clinic or hospital visit) at 2 years and 5 years following the end of study treatment.

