## 10.2 Phase II Expansion Cohort

Screening / baseline evaluations are to be conducted within 2 weeks prior to the start of protocol therapy. Screening labs are used for screening purposes only and Baseline lab values will be considered those obtained on Week 1 Day 1, prior to first study dose injection. Unless otherwise noted study visits will be completed within a  $\pm 1$  week window.

	Screening	W1 	W2	W3	W4	W8	W12	W13	W14	W16	W20	W24	W25	W26	W37	W41	W45	FU 
Confirm eligibility	X 																	
Informed consent	X 																	
KPS	X	X					X	X						X		X		
Physical exam	X	X					X	X					X		X			
CBC w/diff incl. ALC 	X	X	X	X	X	X	X	X	X	X	X	X	X	X	X		X	
CD4	X	X			X	X	X			X	X	X						
LFTs	X	X 			X		X 			X		X 			X 		X	
EKG 	X	X						X					X		X			
Cardiac Enzymes (Tnl or TNT and CK) 	X	X 						X 					X 		X 			
Pregnancy test 	X																	
Brain MRI 																		
SOC MRIs (Q2-3Mo)																		
NANO	X						X									X		
rhIL-7-hyFc 		X						X					X		X			
SOC adjuvant TMZ 					X	X	X			X	X	X						
TMZ drug diary					X	X	X			X	X	X						

Survival X  
AE assessment X ----- X

1. Women of childbearing potential only
2. Given on Days 1-5 of a 28-day cycle for a total of 6 cycles.
3. Within 14 days after the end of SOC RT/TMZ
4. Does not have to occur within 2 weeks prior to the start of protocol therapy; participants may be consented as early as the start of standard of care treatment.
5. Weekly CBC will be performed as per SOC and results will be collected for this study. Weekly CBC will not be performed specifically for this study. They may be drawn at a local lab.
6. Assess survival at 2 years and 5 years following the end of treatment by chart review, phone call, or clinic visit.
7. LFTs must be assessed no more than 7 days prior to each dose of rhIL-7-hyFc/placebo.
8. Eligibility to receive first study dose injection during Week 1 Day 1 will be determined by lab values obtained at Screening, and not reliant on lab values obtained on Day 1
9. In the event of a delay, SOC labs (CBC, LFTs, and/or CD4) coinciding with visits of SOC TMZ dispensing will only be re-drawn if deemed medically necessary per treating physician discretion.

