## 11 DATA SUBMISSION SCHEDULE

Case report forms with appropriate source documentation will be completed according to the schedule listed in this section.

Case Report Form	Submission Schedule
Original Consent Form	Prior to registration
On-Study Form	
Treatment Assignment Form	Prior to starting treatment
Medical History Form	
rhIL-7-hyFc Treatment Form	Every treatment cycle (at W1, W12(Cycle 3), Week 24 (Cycle 6) and Week 37
CBC Form	As per SOC (see study calendar)
NANO Form	
Response Form	To coincide with SOC MRIs (Q2-3 months)
DLT Form	After Cycle 1 for phase I patients only
SOC Treatment Summary Form	At the end of SOC chemoradiation
Research Blood Form	Per Section 9.7 (phase I and randomized phase II patients only)
Research Tissue Form	
Toxicity Form	
Steroid Form	Continuous
Treatment Summary Form	Completion of treatment
Follow Up Form	At Year 2 and Year 5 Follow UP
Progression Form	Time of disease progression (not completed for expansion cohort)
Death Form	Time of death
MedWatch Form	See Section 7.0 for reporting requirements

Any queries generated by Washington University must be responded to within 28 days of receipt by the participating site. The Washington University research team will conduct a regular review of data status at all secondary sites, with appropriate corrective action to be requested as needed.

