### 13.2 Antitumor Effect – RANO

Brain MRI will be performed about every 2 months ( $\pm 30$  days) as per SOC to evaluate response.

**Criteria for response:** Response will be evaluated in this study using the updated response assessment criteria for high-grade gliomas: Response Assessment in Neuro-Oncology (RANO) working group guideline.

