#### **13.4.6 Progression-Free Survival**

PFS is defined as the duration of time from start of treatment to time of progression or death, whichever occurs first.

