#### **15.4.2 Endpoint**

The primary endpoint for the expansion cohort is progression free survival (PFS) defined from date of surgery to date of progression or death due to disease or date of last clinical follow up. The secondary endpoints include AE and OS.

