#### **15.4.3 Sample size calculation**

The sample size calculation was based on testing the estimated median PFS of 11.5 months in the currently enrolled patients versus a null median PFS of 6.3 months (NEJM, 2014, 8:370), assuming PFS follows an exponential distribution.

A two-sided, one-sample log-rank test calculated from N=31 subjects achieves 81.05% power at a 5% significance level to detect a median survival time of 11.5 months (see Section 1.8.2) when the median survival time of the historic control group is 6.3 months, corresponding to a hazard ratio of 0.548. Subjects are accrued for a period of 18 months. Follow-up continues for a period of 12 months after the last subject is added. The probability that a subject experiences an event during the study is 0.7039. The expected number of events during the study with N=31 eligible patients is 22.

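### Expansion-cohort PFS is censored at last clinical follow-up rather than at the last tumour assessment, and no section says how long progression data are collected

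*Combined protocol and SAP*

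**What the plan says.** Section 15.4.2 makes PFS the primary endpoint of the expansion cohort, measured from surgery to "date of progression or death due to disease or date of last clinical follow up". Clinical follow-up is not defined. Section 15.4.5 tests PFS against a 6.3-month median with a two-sided one-sample log-rank test and adds no censoring rule. Nor does the general definition in Section 13.4.6: "PFS is defined as the duration of time from start of treatment to time of progression or death, whichever occurs first".

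On how long tumour status is collected:

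- Section 13.2: "Brain MRI will be performed about every 2 months", as standard care, with no end date.
- Section 11: a Response Form accompanies the standard-care MRIs every 2 to 3 months. No end is given and the expansion cohort is not excluded. The Progression Form is marked as not filled in for this cohort. The Follow Up Form is due at years 2 and 5.
- Section 5.9, at 2 and 5 years after treatment: "All patients will be assessed for survival by phone call, clinic visit, or medical records". Calendar 10.2, footnote 6: "Assess survival at 2 years and 5 years following the end of treatment by chart review, phone call, or clinic visit".
- Section 5.8: "Patients who prematurely discontinue treatment for any reason will be followed as indicated in the study calendar".
- Section 15.4.3: "Follow-up continues for a period of 12 months after the last subject is added", after 18 months of accrual.

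**The concern.** In a one-sample log-rank test, each month a patient is counted as at risk adds ln2/6.3 = 0.110 to the expected events. If nobody is assessing the tumour during that month, a progression in it is either missed or counted only at death. Expected events rise, observed events do not keep pace, and the test moves towards declaring benefit. There is no concurrent control arm in which the same error could cancel.

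Section 15.4.2 permits this, because a patient known to be clinically well some time after the last scan can be counted as progression-free up to that contact. The last numbered visit is Week 45, while the design in Section 15.4.3 needs progression status for 12 to 30 months per patient. The plan does not say who records progression in between, and it drops the form made for that purpose in the one cohort whose primary endpoint is PFS.

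**Working it through.** **1. The plan's own figures (Section 15.4.3).** Inputs: medians 6.3 and 11.5 months, N = 31, accrual 18 months, further follow-up 12 months, exponential PFS.

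- Hazard ratio: 6.3/11.5 = 0.548.
- With L = ln2/11.5, P(event) = 1 − [exp(−12L) − exp(−30L)]/(18L) = 0.7039.
- Events: 31 × 0.7039 = 21.8, stated as 22.
- Power = Φ[(√31·w − 1.96·s0)/s]. Expected events per patient under the null hazard are 0.7039/0.548 = 1.285, so w = 1.285 − 0.704 = 0.581 and s0 = √1.285 = 1.134. With s = 1.202 this gives Φ(0.843) = 80.0%. With s = s0 it gives 81.4%.

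The stated 81.05% lies between these. The sample size is not at fault.

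**2. Timing.** Week 45 is 44 weeks after first dose: 44 × 7/30.4375 = 10.1 months. Section 15.4.2 counts from surgery. Assuming 2 to 3 months from surgery to first dose, Week 45 falls at about 12 to 13 months. A patient whose fourth dose is at Week 37 (36 weeks, 8.3 months) reaches the 2-year survival contact at 8.3 + 24 = 32.3 months after first dose. The longest follow-up in the design is 18 + 12 = 30 months.

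**3. False-benefit error if scans stop while contact continues.** Simulated trials with N = 31, the same accrual, true median 6.3 months and benefit declared if Z < −1.96. Assumptions not in the documents: scans stop 13 months after surgery in a given share of patients, contact continues to the data cut, progression is seen without delay until scans stop, and median survival after progression is 8 months. O and E are observed and expected events.

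| Patients without scans after 13 months | Z = (O−E)/√E | Z = (O−E)/√((O+E)/2) |
|---|---|---|
| None | 1.7% | about 2.5% |
| 25% | 3.3% | 5.2% |
| 50% | 5.8% | 7.9% |
| 100% | 13.5% (12.9–13.5% across repeat runs) | 16.5% |
| Any share, censored at last scan | 1.6–2.0% | 2.5–2.7% |

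The nominal one-tail level is 2.5%. The pattern does not depend on the variance form. With the averaged variance, the 100% figure ranges from 10.8% to 26.3% if scans stop at 15 or 11 months, and from 11.0% to 20.1% if median survival after progression is 4 or 12 months.

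**4. If scanning continues to the data cut.** With the averaged variance, last contact against last scan gives 8.2% − 6.3% = 1.9 points with 2-monthly scans and 13.5% − 10.2% = 3.3 points with 3-monthly scans. The 6.3% and 10.2% come from the spacing of scans, not from the censoring rule.

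**5. The reported median.** Under the null, with scans running to about 13 months, the Kaplan-Meier median stays near 6.3 months under either rule. With a true median of 11.5 months and 25% or 50% of patients unscanned after 13 months, it stays at about 11.5. It shifts materially only in extreme cases: if all scans stopped at 11 months, last-contact censoring gives 13.1.

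**The case against.** A reader might infer that post-treatment follow-up collects survival only, so that PFS is bound to be biased upward. The documents do not support that.

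- MRI about every 2 months (Section 13.2) and the Response Form (Section 11) have no end date. Calendar 10.2 has an MRI row whose marks are not legible in the text reviewed, so it cannot show that scans stop.
- Sections 13.4.3 and 13.4.4 define best response and stable disease as running until progression.
- The RANO table counts clear clinical deterioration as progression, so a contact without a scan can still yield an event.
- Nothing says that a survival phone call counts as clinical follow-up. For patients who receive all four doses, the 2-year call falls outside the 30-month design window. It could fall inside only after early discontinuation, or matter if the data cut came later.
- Counting Week 45 from first dose would make the problem look larger, but Section 15.4.2 counts from surgery.

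All of this stands, and it limits the size of the problem. It does not supply a censoring rule tied to assessment or a stated period for collecting progression data, and it does not explain why the Progression Form is omitted. That the key term is undefined is itself a defect in a primary endpoint.

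**Conclusion.** The point holds as a defect in the endpoint definition and in data capture, with conditional bias towards benefit. Under the documented scan plan, if it is carried through to the data cut, the rule costs roughly 1 to 3 percentage points of false-benefit error. The larger figures, up to about 13%, require scanning to cease while contact continues. The documents neither state nor exclude this, and the figures rest on the assumed 13-month stop and 8-month survival after progression. The exposure lies in the log-rank test far more than in the Kaplan-Meier median.

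A loss of power should not be inferred from the plan as written. It would arise only if scans were not collected after Week 45: with none after 13 months, events under the 11.5-month alternative fall from 21.8 to 16.8, and power from about 82% to 73–74% when censoring is at the last scan. That is why the collection period needs fixing together with the censoring rule.

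**What to change.** - **Section 15.4.2:** censor patients without progression or death at the date of the last adequate MRI/RANO assessment showing no progression. State how a death after a long gap in assessment is handled. The last-scan figures above censor such patients at the last scan; counting those deaths while censoring survivors at their last scan would instead lean against benefit.
- **Section 5.9 and calendar 10.2:** state that standard-care MRI and progression data are abstracted until progression, death or the PFS data cut (12 months after the last enrolment), including after early discontinuation of injections.
- **Section 11:** complete the Progression Form for the expansion cohort.

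While editing, reconcile Sections 15.4.2 and 13.4.6, which also differ on the start date (surgery or start of treatment) and on which deaths count. That is a separate matter.

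The cost is wording, one existing form, and abstraction of scans that patients have as standard care. Some censoring times become shorter, with slightly fewer person-months.

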#### **15.4.3 Sample size calculation**

The sample size calculation was based on testing the estimated median PFS of 11.5 months in the currently enrolled patients versus a null median PFS of 6.3 months (NEJM, 2014, 8:370), assuming PFS follows an exponential distribution.

A two-sided, one-sample log-rank test calculated from N=31 subjects achieves 81.05% power at a 5% significance level to detect a median survival time of 11.5 months (see Section 1.8.2) when the median survival time of the historic control group is 6.3 months, corresponding to a hazard ratio of 0.548. Subjects are accrued for a period of 18 months. Follow-up continues for a period of 12 months after the last subject is added. The probability that a subject experiences an event during the study is 0.7039. The expected number of events during the study with N=31 eligible patients is 22.

#### **15.4.4 Accrual**

We see approximately 150 new patients with HGG (with ~70% are GBM) each year at Washington University with ~30% participating in clinical trials. We expect to be able to enroll approximately 1-2 patient per month on average, and thus we can enroll 31 patients within approximately 18-month accrual period.

#### **15.4.5 Statistical Analysis**

PFS will be analyzed by the KM method and median PFS will be estimated with 95% CI and tested against the null median PFS of 6.3 months by 2-sided one-sample log rank test. OS will be analyzed similarly. Other endpoints will be analyzed similarly as in Section 15.3.5 but without between arm comparison.

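### Section 15.4.5 leaves the variance of the expansion cohort's one-sample log-rank statistic open; naming the averaged form would nearly balance the two tails and add about 4 points of power, by using the benefit-side alpha in full

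*Combined protocol and SAP*

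**What the plan says.** Section 15.4.5 says that median PFS in the expansion cohort will be estimated by Kaplan-Meier and "tested against the null median PFS of 6.3 months by 2-sided one-sample log rank test". Section 15.4.3 sizes the cohort with the same test: "A two-sided, one-sample log-rank test calculated from N=31 subjects achieves 81.05% power at a 5% significance level", with an alternative median of 11.5 months "when the median survival time of the historic control group is 6.3 months, corresponding to a hazard ratio of 0.548", "assuming PFS follows an exponential distribution". On timing it says "Subjects are accrued for a period of 18 months" and "Follow-up continues for a period of 12 months after the last subject is added". It adds: "The probability that a subject experiences an event during the study is 0.7039", which it converts to 22 expected events among 31 patients.

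Neither section says which variance standardises observed minus expected events, how the 5% divides between the two directions, or whether a small-sample correction or exact reference distribution will be used.

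**The concern.** Two forms of the one-sample log-rank statistic concern us here. One divides O-E by the square root of E, the other by the square root of the average of O and E. With a few dozen events they are not interchangeable. The first is skewed, so a cut-off of ±1.96 does not leave 2.5% on each side: too little falls on the benefit side and too much on the harm side.

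Section 1.8.2 gives the cohort's purpose as testing for an improvement in median PFS, so the benefit side is the one that matters. If the standard form is used, part of the error allowance there goes unused, in a design planned at only 81% power. And because the form is not named, it could be chosen after the data are seen, when the two forms may disagree on the cohort's only primary test.

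**Working it through.** **Inputs, all from Section 15.4.3:** null median 6.3 months, alternative 11.5 months, exponential PFS, N=31, 18 months of accrual, 12 months of further follow-up, two-sided 5%. Uniform accrual is an assumption; it reproduces the plan's event probability.

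**Step 1. Reproduce the plan's figures.**
- Hazard ratio: 6.3/11.5 = 0.548, as stated.
- Monthly hazards: L1 = ln 2/11.5 = 0.06027; L0 = ln 2/6.3 = 0.11002.
- Event probability at the alternative: 1 - (e^(-12·L1) - e^(-30·L1))/(18·L1) = 0.7039, as stated. Then 31 × 0.7039 = 21.8 observed events (stated: 22).
- Event probability under the null, same formula with L0: 0.8838, or 27.4 events.
- Mean null-expected count at the alternative: E = 21.82/0.5478 = 39.83.

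**Step 2. Which variance fits 81.05%?**
- Variance E: (39.83 - 21.82)/sqrt(39.83) = 2.854. Power = Φ(2.854 - 1.96) = 81.4%. With the variance of O-E at the alternative taken from simulation, 80.1%.
- Log hazard ratio form: sqrt(22) × |ln 0.548| = 2.82. Power = Φ(2.82 - 1.96) = 80.6%.
- Variance (O+E)/2: (39.83 - 21.82)/sqrt(30.83) = 3.244. Power = Φ(3.244 - 1.96) = 90.0%. With the simulated variance, 85.7%.

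The stated figure agrees with variance E and not with the averaged variance. It does not prove the form, because the log hazard ratio formula also comes close.

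**Step 3. Simulate both forms.** Each trial has 31 exponential PFS times, censored at a uniform 12 to 30 months. O is the number of events, E = L0 × total follow-up, and the cut-off is ±1.96. Two runs of 1,000,000 trials were made for each hypothesis, with power at 9 and 10 months from 400,000 trials each.

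| | (O-E)/sqrt(E) | (O-E)/sqrt((O+E)/2) |
|---|---|---|
| Null, benefit tail | 1.7% | 2.6% |
| Null, harm tail | 3.6-3.7% | 2.3-2.4% |
| Null, total | 5.4% | 4.9-5.0% |
| Power, median 11.5 | 82.7% | 86.4-86.5% |
| Power, median 10 | 61.2% | 67.3% |
| Power, median 9 | 41.0% | 47.5% |

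The gain is about 3.8 points at 11.5 months, 6.1 at 10 and 6.5 at 9.

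**Step 4. Where the gain comes from.** If the standard statistic keeps its variance and its lower cut-off is moved to about -1.82, so that the benefit tail is exactly 2.5%, power is 86.1%. Almost all of the gain is therefore benefit-side alpha that the standard form leaves unspent.

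**Step 5. Robustness.** The scenarios were evenly spaced accrual, accrual over 15.5 or 31 months, follow-up of 6 or 24 months, 10% yearly dropout, complete follow-up, and N of 28 or 34. The standard benefit tail stays at 1.7-1.8% and its harm tail at 3.6-3.7%. The averaged form has 2.4-2.7% and 2.3-2.4%. The gain varies more, from 2.1 points (complete follow-up) to 5.4 points (6 months of follow-up).

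**Step 6. Can the forms disagree on the same data?** With O = 22, the standard form declares benefit when (E - 22)/sqrt(E) > 1.96, that is E above 33.3. The averaged form does so when (E - 22)/sqrt((22 + E)/2) > 1.96, that is E above 32.2. Between these values the primary conclusion depends on the form.

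**The case against.** **No error in the plan is shown.** The test is a recognised one and its power reproduces. A reader might infer that the 81.05% is wrong, or that the documents commit the trial to a test with 1.7% on the benefit side. Neither is supported. The power agrees with the standard form, and reading the plan that way is an inference from that agreement. What stands is that the form is unnamed and that the likely default is skewed.

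**The standard form errs in the safe direction.** Only longer PFS could support a claim of efficacy, and there the standard form is below 2.5%. Its excess over 5% lies wholly in the harm tail. This is correct. No false-positive risk is being missed, and what is lost is power.

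**The gain is not free.** This stands. Benefit-side false positives rise from about 1.7% to 2.6%, slightly above 2.5%. It would be wrong to present the change as costless.

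**The null may not hold.** A reader might infer that the averaged form makes the 5% level accurate, but that is true only within the model. Section 15.4.2 starts PFS at surgery (Section 13.4.6 says start of treatment), while Section 15.5 counts only patients who received a dose, and Section 5.2 places the first dose after radiation and temozolomide. Suppose, as an assumption, that each patient has a guaranteed event-free interval before the first dose, counted in PFS without adjustment. Benefit-side error is then 9.9% (standard) and 13.4% (averaged) for 1.5 months, and 33.6% and 40.9% for 3 months. Section 1.8.2 also cites medians of 5.4 and 7.3 months by molecular profile. If the true median without benefit were 7.3 months, a test against 6.3 would declare benefit in 9.5% and 12.8% of trials. These are larger problems than the choice of variance, and the averaged form is somewhat further from nominal under them. But they inflate error under both forms and need their own remedies. A skewed statistic does not correct them.

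**Conclusion.** The point holds as a cheap improvement, not as an error in the sample size calculation. If the standard form is used, as the stated power suggests, about two-thirds of the total error (3.7 of 5.4 points) falls in the direction that the cohort was not set up to test. The averaged variance brings both tails close to 2.5% and raises power from 82.7% to about 86.5% at the planned alternative, with about 6 points more at a true median of 9 to 10 months. Such medians deserve attention because the 11.5-month alternative is the median seen in only 12 phase I patients (Section 1.8.2).

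The figures rest on exponential PFS, uniform accrual, the planned follow-up and a valid 6.3-month null measured from a valid time origin. The tail imbalance is stable across the scenarios tried; the size of the gain depends on follow-up.

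**What to change.** In Section 15.4.5, before the PFS analysis, state that the primary test uses Z = (O-E)/sqrt((O+E)/2), where O is the number of observed PFS events and E is the sum over patients of the null cumulative hazard at each patient's follow-up time (ln 2/6.3 per month under the exponential null), with two-sided 5% and cut-offs of ±1.96. Report (O-E)/sqrt(E) as a sensitivity analysis.

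The cost is one sentence, with no added patients, follow-up or data. The price is a benefit-side error of about 2.6% in place of 1.7%, and the text should say so. The 81.05% in Section 15.4.3 can stay, with a note of the variance it assumes. The PFS time origin and the choice of null median should be settled separately, since the error rates of either form depend on them.
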